12. STATISTICAL METHODS AND DETERMINATION OF SAMPLE SIZE

The objectives of the study and the endpoints to be analyzed are listed in Section 4.

12.1. General Considerations

The study is conducted to evaluate the efficacy and safety of BIIB122 in participants with early-stage PD who carry a pathogenic LRRK2 variant. Detailed methodology for summary and statistical analyses of the data collected in this study are outlined here and further detailed in a SAP, which will be maintained by the sponsor. If there are discrepancies between the description of the statistical methods between the protocol and the SAP, the SAP will override the protocol.

12.2. Analysis Sets

FAS: all randomized participants who receive at least 1 dose of study treatment.

Safety analysis set: all randomized participants who receive at least 1 dose of study treatment.

[REDACTED]

[REDACTED]

[REDACTED]

12.3. Methods of Analysis for Efficacy Endpoints

12.3.1. Analysis of the Primary Endpoints

The primary efficacy endpoint is time to confirmed worsening in MDS-UPDRS Parts II and III combined score over the treatment period. Confirmed worsening is defined as

[REDACTED]

[REDACTED]

[REDACTED]

[REDACTED]

CONFIDENTIAL

The information contained herein may not be used, disclosed, or published without the written consent of Biogen MA Inc.

[REDACTED]

[REDACTED]

[REDACTED]

[REDACTED]

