Sample Size Determination: A minimum of approximately [REDACTED] events would be required to detect a [REDACTED] relative treatment effect for BIIB122 [REDACTED] for the primary endpoint with [REDACTED] power, at the 2-sided significance level of [REDACTED]. Up to 2 potential interim efficacy analyses, pending regulatory feedback, may be conducted in which case approximately [REDACTED] events would be needed to achieve approximately [REDACTED] power for the study. With a sample size of approximately [REDACTED] participants per treatment group, followed for a minimum of [REDACTED] weeks ([REDACTED] weeks of treatment followed by [REDACTED] weeks of SFU) and a maximum of

CONFIDENTIAL

The information contained herein may not be used, disclosed, or published without the written consent of Biogen MA Inc.

█ weeks (█ weeks of treatment followed by █ weeks of SFU), a total number of up to █ events is expected to have been reached when all participants complete the planned treatment period and provides the study with approximately █ power with 2 potential IAs. These estimates assume a median time to confirmed worsening of █ weeks (approximately █ months) in the placebo group, and a █ annual exponential dropout/censoring rate.

Visit Schedule:

Study assessments conducted at each visit are listed in the Schedule of Activities ([Table 1](#)).

Duration of Study Participation:

The total study duration for each participant (including the Screening period) will be a minimum of approximately 103 weeks and a maximum of approximately 187 weeks as follows:

- 5-week Screening period █
- 96-week minimum to 180-week maximum (when the total number of events for the primary endpoint reaches approximately 200 events) double-blind, placebo-controlled treatment period
- █

Benefit-Risk Analysis:

There is a significant need for an effective disease modifying therapy that delays PD progression, which is not addressed by current therapies. Lysosomal dysfunction contributes to disease risk in PD patients, suggesting that therapeutics that reduce LRRK2 kinase activity may provide benefit for patients with PD.

The data from previous clinical studies with doses of up to 300 mg QD in participants with PD (28 days exposure), and up to 400 mg BID in healthy volunteers (14 days exposure)

CONFIDENTIAL

The information contained herein may not be used, disclosed, or published without the written consent of Biogen MA Inc.

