²Screening assessments can be performed over approximately 2 days (need not be consecutive) to minimize participant burden. The overall screening window will be increased by 7 days to a maximum of 42 days for participants in the [REDACTED] to allow enough time to complete assessments.

³Baseline visit may be split over 2 consecutive days when deemed necessary by Investigator. Dosing and timed assessments must be performed on the second baseline visit day.

⁴The EOT Visit is scheduled to align with a participant's last dose. If a participant discontinues study treatment but remains in the study, the EOT Visit will occur at the next scheduled visit. Participants who permanently discontinue study treatment early will be encouraged to continue study participation, maintaining the same schedule of study assessments as participants continuing in the double-blind treatment period. The ET Visit will occur if a participant withdraws from the study.

[REDACTED]

[REDACTED]

⁷Where applicable, postmenopausal status must be confirmed as follows: for women \leq 55 years of age, 52 continuous weeks of natural (spontaneous) amenorrhea without an alternative medical cause and a serum FSH level \geq 40 mIU/mL; for women $>$ 55 years of age, 52 continuous weeks of natural (spontaneous)

CONFIDENTIAL

The information contained herein may not be used, disclosed, or published without the written consent of Biogen MA Inc.

amenorrhea without an alternative medical cause and a serum FSH level ≥ 40 mIU/mL, or at least 5 continuous years of natural (spontaneous) amenorrhea without an alternative medical cause.

⁸For women of childbearing potential, a serum pregnancy test will be performed at Screening, [REDACTED], EOT/ET Visit, and the SFU Visit; a urine pregnancy test will be performed at other study visits as indicated.

⁹The single genetic testing sample collected at Screening will be sent to the central genetics laboratory for all participants and will be used for both eligibility and exploratory genomics (See Section 9.5).

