4. STUDY OBJECTIVES AND ENDPOINTS

Primary Objective	Primary Endpoint
To evaluate the efficacy of BIIB122 225 mg compared with placebo, based on the time to confirmed worsening in MDS-UPDRS Parts II and III combined score	Time to confirmed worsening in MDS-UPDRS Parts II and III over the treatment period (minimum 96 weeks and maximum 180 weeks)
Secondary Objectives	Secondary Endpoints
To evaluate the safety and tolerability of BIIB122 225 mg compared with placebo when administered for 96 to 180 weeks	Incidence of AEs and SAEs
To evaluate the efficacy of BIIB122 225 mg compared with placebo, based on the time to confirmed worsening in MDS-UPDRS Part II score	Time to confirmed worsening in MDS-UPDRS Part II score over the treatment period
To evaluate the efficacy of BIIB122 225 mg compared with placebo, based on change in the MDS-UPDRS Parts II and III combined score, when administered for 96 weeks	Change in MDS-UPDRS Parts II and III combined score from Baseline to Week 96
To evaluate the efficacy of BIIB122 225 mg compared with placebo, based on change in mSE-ADL score	Time to confirmed worsening in mSE-ADL score over the treatment period
To evaluate the efficacy of BIIB122 225 mg compared with placebo, based on change in MDS-UPDRS Parts I, II, and III combined score	Change in MDS-UPDRS Parts I, II, and III combined score from Baseline to Week 96

[figure not shown]
CONFIDENTIAL

The information contained herein may not be used, disclosed, or published without the written consent of
Biogen MA Inc.

CONFIDENTIAL

The information contained herein may not be used, disclosed, or published without the written consent of
Biogen MA Inc.

CONFIDENTIAL

The information contained herein may not be used, disclosed, or published without the written consent of
Biogen MA Inc.

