8. DISCONTINUATION OF STUDY TREATMENT AND WITHDRAWAL OF PARTICIPANTS FROM THE STUDY

8.1. Discontinuation of Study Treatment

Study treatment interruption is discussed in Section [7.2](#).

The use of disallowed concomitant therapies, described in Section [7.7.1.3](#), will lead to study treatment discontinuation, at the discretion of the Investigator and/or Medical Monitor.

A participant *must* permanently discontinue study treatment for any of the following reasons:

- The participant becomes pregnant. Study treatment must be discontinued immediately. Report the pregnancy according to the instructions in Section [11.4.1](#).
- The participant withdraws consent to continue study treatment.
- The participant experiences an AE that necessitates permanent discontinuation of study treatment.
- The participant experiences a medical emergency that necessitates unblinding of the participant's treatment assignment.
- The participant requires use of [REDACTED] or requires prolonged (≥ 1 month) use of [REDACTED]
- At the discretion of the Investigator for medical reasons.

The primary reason for discontinuation of study treatment must be recorded in the participant's eCRF.

The ET Visit will occur if a participant withdraws from the study.

If a participant discontinues study treatment but remains in the study, the EOT Visit will occur at the next scheduled visit. Participants who permanently discontinue study treatment early will be encouraged to continue study participation, maintaining the same schedule of study assessments as participants continuing in the double-blind treatment period.

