12.9. Interim Analyses

Up to 2 IAs, one earlier and one later in the study, pending regulatory feedback, may be performed for efficacy over the course of the study. A Lan-Demets alpha-spending function will be used to approximate the O'Brien Fleming for the interim and final analysis, to control the overall type I error alpha level at 0.05 two-sided. Additional details will be described in the SAP.

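### Does counting the primary endpoint over the treatment period drop worsening that occurs after a participant stops study drug?

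*Combined protocol and SAP*

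**What the plan says.** Section 12.3.1 sets the endpoint: "The primary efficacy endpoint is time to confirmed worsening in MDS-UPDRS Parts II and III combined score over the treatment period". The definition of confirmed worsening and the rest of that section are blacked out, as is all of Section 12.3.2 on the secondary endpoints.

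Section 4 puts numbers on the window: "over the treatment period (minimum 96 weeks and maximum 180 weeks". The Synopsis uses the same numbers for the planned double-blind phase: "96-week minimum to 180-week maximum (when the total number of events for the primary endpoint reaches approximately 200 events".

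Footnote 10 to Table 1 (Section 1.3) starts the treatment period at randomization and closes it when the participant takes the last dose. The rest of that footnote covers blister wallets, on-site dosing and tablet counts.

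For participants who stop drug early, Section 8.1 says: "Participants who permanently discontinue study treatment early will be encouraged to continue study participation, maintaining the same schedule of study assessments". Footnote 4 to Table 1 and Section 5.2 say the same.

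Section 12.1 gives the SAP precedence over the protocol on statistical methods. The supplied file contains no SAP text on the primary analysis.

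**The concern.** Put footnote 10 beside Section 12.3.1 and the endpoint window seems to shut at last dose. A participant who stops drug at week 20 would leave the primary analysis then, although later visits are scheduled. A worsening first seen on drug but confirmed after stopping would not count. The two time-to-worsening secondary endpoints (MDS-UPDRS Part II and mSE-ADL) carry the same phrase.

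If that were the rule, it would matter. In a progressive disease, stopping drug may be linked to worsening or to poor tolerability, so censoring at last dose could be informative and could disturb the randomised comparison. It would also discard collected data and remove events from an event-driven design.

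**Working it through.** **1. Which window does the endpoint use?** Take a participant who stops drug at week 20.

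| Source | Length of the treatment period |
|---|---|
| Table 1, footnote 10 | 20 weeks |
| Section 4 and Synopsis | at least 96 weeks |

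Both cannot hold. The 96 and 180 weeks are planned lengths, as the duration arithmetic shows. With 5 weeks of screening (Synopsis) and a safety visit 2 weeks after last dose (Section 5.1), 5 + 96 + 2 = 103 and 5 + 180 + 2 = 187. These are the minimum and maximum participant durations in Section 5.2. The numbers attached to the endpoint are therefore those of the planned double-blind period, not of an individual's time on drug.

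**2. Is the plan's event target sound?** The visible inputs are about 200 events (Synopsis), 1:1 allocation, and interim analyses designed "to control the overall type I error alpha level at 0.05 two-sided". The hazard ratio is blacked out in Section 12.10. I assume 0.65, from the 35% effect in Section 3.1.2.

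Schoenfeld power = Φ(½√d × |ln HR| − 1.96). With d = 200: ½ × 14.142 × 0.4308 − 1.96 = 1.086, and Φ(1.086) = 0.861. For 85% power the same formula needs 194 events, or about 198 with an assumed 2% inflation for the interim analyses. The target of 200 fits roughly 85% power. The stated power is blacked out, so it cannot be matched directly.

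**3. What would last-dose censoring cost if it applied?** Assumptions: 200 per arm, follow-up uniform on 96 to 180 weeks, placebo median 104 weeks, HR 0.65, dropout 5% a year. Expected events per arm = 200 × the mean over follow-up T of λ/(λ+ω) × (1 − e^(−(λ+ω)T)). Here λ = ln 2/104 per week on placebo and 0.65 times that on active. Annual rates r convert to weekly hazards as −ln(1−r)/52. ω is the dropout hazard, plus the discontinuation hazard if events after last dose are lost.

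| Annual discontinuation | Expected events | Power |
|---|---|---|
| none lost | 197 | 0.855 |
| 3% | 190 | 0.843 |
| 5% | 186 | 0.835 |
| 10% | 175 | 0.813 |
| 15% | 165 | 0.789 |

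Power is taken from unrounded events. With placebo medians from 78 to 156 weeks, the loss of events runs from about 3% to 17% over the same discontinuation rates.

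**4. What would bias require?** If fractions a (active) and p (placebo) of would-be events are censored just before they count, the estimated hazard ratio is about the true one × (1−a)/(1−p). Simulation (log-rank, 4000 replicates, 200 per arm, placebo median 101 weeks, 5% annual dropout) gave:

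| True HR | Lost, active / placebo | Formula | Simulated HR | Rejection rate |
|---|---|---|---|---|
| 1.00 | 15% / 5% | 0.85/0.95 = 0.895 | 0.895 | 12.2% |
| 1.00 | 10% / 5% | 0.90/0.95 = 0.947 | 0.946 | 6.2% |
| 1.00 | 10% / 10% | 1.00 | – | 5.1% |
| 0.65 | 5% / 15% | 0.65 × 0.95/0.85 = 0.726 | 0.725 | 57.6% |

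Equal loss does no harm to type I error. The large figures come from a threefold imbalance that is assumed, not documented.

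**The case for a change.** The strongest case for the concern is textual. Footnote 10 is the only visible statement of when the period starts and ends. Footnote 4 describes discontinuers as "maintaining the same schedule of study assessments as participants continuing in the double-blind treatment period", which sets them apart from people still in that period and so favours the last-dose reading. Redaction does not remove the tension: if the hidden rule counts events after last dose, it conflicts with footnote 10; if it does not, the concern is right. Unequal discontinuation is also conceivable. Section 3.2.3 reports two participants in the Phase 1b study who stopped drug for an adverse event, both on BIIB122.

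Part of this stands. The term has two senses, and the visible text does not say which one governs the endpoint. The rest does not carry. A conflict with a footnote about dosing and adherence would not alter the primary result. Keeping discontinuers on the full efficacy schedule fits a plan to use those data at least as well as a plan to discard them. Two participants in a 28-day study do not establish differential loss over 96 to 180 weeks. The power cost is also softened in two ways: Sections 5.1 and 5.2 tie study duration to reaching the event target, and Section 12.10 assumes a single combined dropout and censoring rate, which may already allow for treatment-related censoring.

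**Conclusion.** No change to the plan follows. This is loose use of a term, and the gap is one the analyst fills when writing the censoring rule. That rule belongs in the blacked-out part of Section 12.3 or in the SAP, which overrides the protocol. The endpoint's own 96-to-180-week window and the continued visits both point to the planned double-blind period, and no visible sentence excludes worsening after last dose.

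Rewriting the endpoint would impose a strategy for discontinuation without sight of the sponsor's own. Running the window to the last study assessment would also move it beyond last dose, to the safety visit two weeks later, for participants who complete treatment.

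The figures describe a hypothetical rule: a loss of about 2 to 7 percentage points of power at 5% to 15% annual discontinuation, and type I error of 6.2% to 12.2% only under assumed unequal loss. They rest on an assumed hazard ratio, placebo median, dropout rate and discontinuation rate. The conclusion would need another look only if the unseen text does censor at last dose.

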12.3.2. Analysis of Secondary Endpoints

[REDACTED]

[REDACTED]

[REDACTED]

[REDACTED]

[REDACTED]

[REDACTED]

CONFIDENTIAL

The information contained herein may not be used, disclosed, or published without the written consent of
Biogen MA Inc.

A large black rectangular redaction box covers the majority of the page content, starting below the header and ending above the footer. The redaction is not perfectly uniform, with some white space visible at the top and bottom edges.

12.7. Methods of Analysis for Safety Endpoints

12.7.1. Adverse Events

AEs will be coded using the Medical Dictionary for Regulatory Activities. Any safety data collected from in-clinic or remote visits will be included in the statistical analysis.

All analyses of AEs will be based on the principle of treatment emergence. An AE is considered to be treatment emergent if it has an onset date on or after the date of first dosing, or if it was present prior to the first dose and subsequently worsened. Incidences of all AEs will be presented by system organ class and preferred term, by treatment group, and by visit. In addition, incidences of all AEs by severity, by relationship to study treatment [REDACTED]

will be presented. Data after participants started symptomatic PD medications will be analyzed both ways (included and excluded).

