11.3. Monitoring and Recording Events

11.3.1. Adverse Events

Any AE experienced by the participant between the time of first dose of study treatment and safety follow up is to be recorded on the eCRF, regardless of the severity of the event or its relationship to study treatment, [REDACTED]

[REDACTED] Nonserious AEs that occur during the Screening period and that are assessed by the Investigator as related to the ligand will be captured by the sites on the AE eCRF. At each study visit, the Investigator will assess the participant for AEs and will record any new AEs or updates to previously reported AEs on the eCRF.

CONFIDENTIAL

The information contained herein may not be used, disclosed, or published without the written consent of Biogen MA Inc.

AEs that are ongoing when the participant completes or discontinues the study will be followed by the Investigator until the event has resolved, stabilized, or returned to baseline status. AE outcome will not be recorded on the eCRF.

- [REDACTED]
- [REDACTED]
- [REDACTED]

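### The treatment-emergent AE definition has no end date, so off-drug events in participants who stop early but stay in the study would be pooled with on-drug events

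*Combined protocol and SAP*

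**What the plan says.** Section 12.7.1 sets the rule for all AE summaries: "All analyses of AEs will be based on the principle of treatment emergence". It then defines the term: "An AE is considered to be treatment emergent if it has an onset date on or after the date of first dosing". An event already present before dosing also counts if it worsens later. The definition is an unbroken sentence with no upper limit. The section adds: "Any safety data collected from in-clinic or remote visits will be included in the statistical analysis". It also commits to analysing data after the start of symptomatic PD medication both with and without those data. The visible text makes no such split at the stop of study drug.

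On follow-up, Section 8.1 says: "Participants who permanently discontinue study treatment early will be encouraged to continue study participation, maintaining the same schedule of study assessments". Sections 5.2 and 1.3 (Table 1, footnote 4) repeat this. Section 12.2 keeps everyone with at least one dose in the safety analysis set.

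On collection, Section 11.3.1 says two things. One is a window: "Any AE experienced by the participant between the time of first dose of study treatment and safety follow up is to be recorded". The other is a visit rule: "At each study visit, the Investigator will assess the participant for AEs and will record any new AEs". Section 5.1 places the SFU visit 2 weeks after the last dose.

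**The concern.** The safety objective in Section 4 concerns the drug as administered for 96 to 180 weeks. If a participant stops drug early and stays, new AEs during the off-drug visits fall under the definition and enter the same tables as on-drug events. For an effect that ceases when the drug stops, off-drug onsets arise at about the background rate in both arms, which pulls the active-to-placebo incidence ratio towards 1. The protocol already accepts the idea of a split at a change in treatment, because it makes one at the start of symptomatic PD medication. A split at the stop of study drug bears more directly on the safety objective.

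**Working it through.** **1. The plan's own durations.** Screening is 5 weeks and treatment 96 to 180 weeks (Synopsis); SFU is 2 weeks after the last dose (Section 5.1).
- 5 + 96 + 2 = 103 weeks and 5 + 180 + 2 = 187 weeks, as in Section 5.2.
- 96 + 2 = 98 weeks, as in Section 5.5.

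For a participant who completes treatment, the off-drug tail is therefore 2/98 = 2.0% to 2/182 = 1.1% of follow-up from first dose.

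**2. Off-drug time for early discontinuers who stay.** Stopping at week s leaves 96 − s to 180 − s weeks.
- Week 12: 84 to 168 weeks.
- Week 24: 72 to 156 weeks.
- Week 48: 48 to 132 weeks.

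**3. Effect on the incidence ratio.** The documents show no AE rate and no discontinuation rate, so these inputs are assumptions:
- placebo rate λ = 0.05 per year;
- on-drug rate ratio r = 2, returning to 1 on stopping;
- follow-up T = 138/52 = 2.654 years (138 is the midpoint of 96 and 180 weeks);
- discontinuation at rate d per year in both arms, with everyone who stops staying to T.

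Formulas, with a = d + rλ and b = d + λ:
- Open window, placebo: 1 − exp(−λT).
- Open window, active: 1 − [exp(−aT) + d·exp(−λT)·(1 − exp(−(a − λ)T))/(a − λ)].
- Cut at last dose, active: (rλ/a)(1 − exp(−aT)).
- Cut at last dose, placebo: (λ/b)(1 − exp(−bT)).

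Reference with nobody stopping: 23.31% against 12.43%, ratio 1.88.

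| d per year | Window | Active | Placebo | Ratio | Difference (points) |
|---|---|---|---|---|---|
| 10% | open | 22.01% | 12.43% | 1.77 | 9.6 |
| 10% | cut | 20.59% | 10.95% | 1.88 | 9.6 |
| 20% | open | 20.92% | 12.43% | 1.68 | 8.5 |
| 20% | cut | 18.30% | 9.70% | 1.89 | 8.6 |

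**4. Sensitivity to who stays.** At d = 20% per year, 1 − exp(−0.2 × 2.654) = 41% have stopped by week 138. If only half of them stay, each arm's incidence is the average of its open and cut values: active (20.92 + 18.30)/2 = 19.61%, placebo (12.43 + 9.70)/2 = 11.06%, ratio 1.77.

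**5. A second model.** Assume 96 weeks of follow-up, a placebo risk of 10%, rate ratio 2, a share of each arm stopping at week 48 and staying, 200 per arm, and a cut at last dose plus 2 weeks. For a share of 20%:
- Open, active: 0.8 × 0.190 + 0.2 × (1 − 0.9^1.5) = 0.181, against placebo 0.100, ratio 1.81.
- Cut: 0.172 against 0.091, ratio 1.90.

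| Share stopping | Ratio, open | Ratio, cut | Power, open | Power, cut |
|---|---|---|---|---|
| 10% | 1.86 | 1.90 | 68.8% | 70.2% |
| 20% | 1.81 | 1.90 | 64.8% | 67.8% |
| 30% | 1.77 | 1.90 | 60.5% | 65.2% |

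At 20% the risk difference is 8.1 (open) against 8.2 points (cut).

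**The case against.** The strongest reply is that collection has its own end. Section 11.3.1 records AEs up to safety follow-up, and Section 5.1 puts that visit 2 weeks after the last dose for each participant. Taken literally, no late event can enter for anyone. This settles the matter for those who complete treatment. For early discontinuers it does not: Section 11.3.1 also requires new AEs to be recorded at each study visit, and Section 8.1 keeps these participants on the same schedule. If the first reading governs, there is no dilution, but the protocol does not say what happens to AEs at their later visits. If the second governs, the dilution above applies.

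A reader might infer that the open-ended analysis is the only one planned. The file does not show that. Text is redacted within the list of AE summaries in Section 12.7.1 and after the collection window in Section 11.3.1. Section 12.1 defers detail to a SAP that overrides the protocol, and that SAP's AE text is not in the file. Visible summaries also include AEs by visit and by relationship to treatment. What stands is that the definition itself is unredacted and, unlike Sections 12.7.3, 12.7.5 and 12.7.6, Section 12.7.1 does not refer its definition to the SAP.

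A reader might also infer that any drug-related signal is weakened. Incidence counts onsets, so an on-drug event that later resolves is still counted, as is an on-drug AE that leads to stopping. Only new off-drug onsets dilute. A delayed or persistent effect could be missed by a cut-off, so the open window has value of its own.

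**Conclusion.** The point holds in a limited form and is a cheap improvement. As written, the definition would label off-drug onsets in early discontinuers who stay as treatment-emergent, and no visible analysis separates them. The protocol is also unclear on when AE collection ends for these participants.

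Under the first model the incidence ratio is 1.77 rather than 1.88 at 10% per year discontinuation, and 1.68 rather than 1.89 at 20%. The second model costs about 1 to 5 points of power when 10% to 30% stop. These sizes rest on assumed AE and discontinuation rates, on an effect that ceases at stopping, and on AEs being collected throughout off-drug follow-up.

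It would be tempting to say that 22% of the excess is lost at 20% per year, from (1.876 − 1.683)/0.876. That holds on the ratio scale only, against a benchmark in which nobody stops. The risk difference is 8.5 points open and 8.6 cut, because the smaller absolute excess comes from shorter exposure and not from the definition.

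**What to change.** In Section 12.7.1, and in the SAP so that the two agree:
- Add an on-treatment summary of AEs with onset or worsening from first dose through last dose plus the protocol's own 2-week SFU interval.
- Tabulate events after that window separately, by arm.
- Keep the open-ended whole-study summary, so that delayed effects are not lost.

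Reconcile Sections 5.1, 8.1 and 11.3.1 so that they state when AE collection ends for participants who stop drug early and remain in the study. If the SAP already has an end date, the protocol should match it.

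The cost is a short change of wording and one extra set of AE tables to present. Sample size and the efficacy analyses are unaffected.
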